## 7. INTERIM MONITORING PLAN

## 7.1 Overview

Interim monitoring will focus on patient accrual, baseline comparability of treatment groups in terms of demographic and clinical characteristics, protocol adherence, loss to follow-up, data completeness and quality, and safety.

# 7.2 Monitoring of Safety

Details of the safety and adverse event monitoring plan were provided in the study protocol. This is a minimal risk trial. Adverse and serious adverse events will be collected. Unanticipated problems will also be reported to the Medical Safety Monitor.

## 8. ANALYTIC PLAN

## 8.1 Overview

The analysis of the primary and secondary outcomes will be according to the principle of intent-to-treat, i.e., participants will be analyzed according to their original treatment assignment regardless of adherence to protocol. SAS 9.4, MPlus, and R 3.0.2 software will be used for all analyses.

# 8.2 Comparability of Treatment Groups

Comparability of treatment groups will be assessed by comparing the distribution of baseline characteristics in the two groups using appropriate graphical procedures, summary statistics and multivariate methods. The randomization is designed to produce balance on important covariates and baseline levels of the outcome measures. Nonetheless, some degree of prerandomization imbalance in study outcomes may occur, and we regress post-randomization observations on baseline scores to adjust for such imbalance.

## 8.3 Analysis of the Primary Outcomes

Effects of treatment on opioid misuse and chronic pain symptoms will be evaluated using linear and nonlinear mixed models with fixed effects consisting of a time factor and between-subjects treatment factor (MORE vs. SG), and will adjust for randomization imbalance by covarying baseline levels of the outcome. For the continuous pain symptom outcome measured by the

Brief Pain Inventory (BPI), the longitudinal trajectory for individual i on outcome j in treatment group g at post-randomization time t is modeled, under the full-rank parameterization, as

$$(1) \ \ y_{ijg,t>1} = a_{ijg} + \beta y_{ijg,t=1} + \mu_{jg,t>1} + \varepsilon_{ijg,t>1} \ \ , \ \ a_{ijg} \sim N(0,\psi_j) \ , \varepsilon_{ijg,t>1} \sim MVN(0,\Theta_j) \ ,$$

 $a_{ijg}$  is a random intercept with zero mean and variance  $\psi_i$ ,

 $\beta$  is the fixed regression coefficient of the post measures on pre-randomization baseline (time 1) score  $y_{ii\alpha,t}$ =1

 $\mu_{jg,t>1}$  are the post-randomization treatment arm means at times 2 through 5, conditioned on baseline, equivalent in this parameterization to distinct intercept terms

 $\mu_{jgt>1} = E(y_{ijg,t>1} \mid a_i, y_{ijg,t=1})$  for each group and time, and  $\epsilon_{ijg,t>1}$  are multivariate normal random error terms assumed to follow either an independent scaled diagonal or AR1 error structure, as determined by comparison of BIC model statistics.

Opioid misuse as measured by the Drug Misuse Index (DMI) is a dichotomous longitudinal variable Y, and we will evaluate treatment impact with a generalized linear mixed model specifying a binary distribution and logit link, with time t and group g as categorical factors and a random intercept  $\zeta_i$ :

$$\log(\pi_i / (1 - \pi_i)) = \alpha_g + \beta_t + \gamma_{gt} + \zeta_i$$

$$Y_{igt} \mid \zeta_i \sim Bernoulli(\pi_{igt}), \ \zeta_i \sim iid \ N(0, \psi)$$

For the opioid misuse outcome (Drug Misuse Index; DMI), it is not necessary to adjust for baseline differences, as all participants exhibited opioid misuse at baseline.

Our primary interest lies in estimating, for the BPI co-primary pain outcome j, the adjusted main effect, which represents the overall benefit of treatment across all four post-treatment measurement points conditional on baseline:

(2) 
$$\hat{\delta}_j = (1/4) \sum_{t=2}^{t=5} \hat{\mu}_{g=SG,t} - \hat{\mu}_{g=MORE,t}$$
, a linear combination over the four post-randomization (t>1) adjusted treatment means. The key estimand for binary DMI will be the main effect on the additive logit scale over the four post-randomization occasions.

This estimand is meaningful whether a time-by-treatment arm interaction is present or not, as it represents the expected overall treatment benefit for individuals randomly selected from the two populations. The null hypothesis of no treatment impact is  $H_{0j}$ :  $\delta_j = 0$ , a single numerator

degree-of-freedom test, which we evaluate at alpha=.05/3 = .0167 (i.e., Bonferroni adjustment for the three primary variables) under restricted maximum likelihood with Kenward-Roger denominator degrees of freedom. To control for false discovery in the three primary outcomes, we will compare the unadjusted p-values against Bonferroni-adjusted alpha =.05/3 = .0167.

The analysis of primary outcomes achieves unbiased estimates of model parameters when missingness arises from processes that depend on observed covariates (Missing at Random, or MAR). Maximum likelihood estimation (MLE) procedures under an intent-to-treat philosophy are robust against common patterns of missing data. MLE is based on all data observations; no values are deleted or imputed. In our tables and reporting, we refer to the p-values under the standard MAR assumption as pMAR. There is however no definitive test for the MAR assumption. But we investigate sensitivity to missing data and possible other covariates using two other approaches. We extend the scope of the MAR analysis using Full Information (Direct) Maximum Likelihood under broader multivariate patterns of missingness, incorporating simultaneous longitudinal outcomes and key sociodemographic variables as auxiliary variables correlated with the outcome. In simulations, this approach often yields performance equal to or better than achieved by multiple imputation and explicit nonignorable missingness models. All analyses will be conducted with the latent variable modeling program MPlus, which

incorporates full information maximum likelihood estimation in multivariate models. The global hypothesis test will be examined under three sensitivity variations:

- a) Replication of the analysis model (1) under simultaneous inclusion of the three primary outcomes of drug misuse, pain severity, and pain interference, repeated over post-randomization assessments, along with respective baseline predictor values. In this multivariate analysis, pain severity and pain interference are continuous variables, while drug misuse is represented as a dichotomous outcome under a logit link. All three outcomes are free to correlate in the analysis, with the global hypothesis test imposed by nonlinear equality constraints on the net benefits  $H_{0j}$ :  $\delta_j = 0$  for j=1,2,3, a 3 df test.
- b) Replication of the 3 df global hypothesis test in (a) with the addition of the continuous log-transformed opioid use secondary outcome, and the continuous Distress secondary outcome as correlated variables.
- c) Replication of (b) with the addition of the demographic predictor variables gender and continuous age at baseline.
- (d-f) Re-running variations a, b, and c under constrained longitudinal analysis (CLDA) rather than regression adjustment for baseline. Under CLDA, the baseline means are constrained to be equal across arms. These constraints are straightforward under multivariate modeling. The overall benefit contrasts among the post-baseline means, conditional on within-outcome baseline treatment arm equalities, are equivalent to the difference in areas under the curve for the conditional post-baseline mean trajectories.

In the text and tables, we report p-values obtained under Model C as  $p_{MAR^+}$ , to indicate that the standard MAR analysis has been supplemented with several auxiliary variables, as described above.

Finally, we re-estimated all analyses under a simple selection model  $^{37,38}$  in which missingness is dependent on the value of the unobserved outcome in as well as the prior observed responses. In the text and table, we report p-values obtained under this model as  $p_{NMAR}$ . The Not Missing at Random designation indicates that this model does not require the more restrictive assumptions of MAR, but may be valid when missingness depends on underlying and unobserved values.

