## **Table of Contents**

- 1. BACKGROUND
- 2. AIMS
- 3. STUDY DESIGN
- 4. ENDPOINTS
  - 4.1 Primary
  - 4.2 Secondary
  - 4.3 Tertiary
- 5. RANDOMIZATION
  - 5.1 Method of Randomization
  - 5.2 Allocation Concealment
- 6. SAMPLE SIZE
  - 6.1 Preliminary Data
  - 6.2 Sample Size Determination for Primary Outcome
  - 6.3 Power for Secondary Outcomes
  - 6.4 Power for Tertiary Outcomes
- 7. INTERIM MONITORING PLAN
  - 7.1 Overview
  - 7.2 Trial Adaptation Guidelines
  - 7.3 Monitoring Inter-practice Variation
  - 7.4 Monitoring of Efficacy and Futility
  - 7.5 Monitoring of Safety
- 8. ANALYTICAL PLAN
  - 8.1 Overview
  - 8.2 Comparability of Treatment Groups
  - 8.3 Analysis of Primary Outcome
  - 8.4 Analysis of Secondary and Tertiary Outcomes

Title	Mindfulness-Oriented Recovery Enhancement for Opioid Misuse and Chronic Pain in Primary Care: A Randomized Controlled Trial
Study Design	The design is a parallel group superiority trial. The unit of randomization is the individual patient.
Study Duration	5 years.
Trial Sites	University of Utah Health – Community Physicians Group.
Objective	Conduct a randomized controlled trial to determine the efficacy of a Mindfulness-Oriented Recovery Enhancement intervention for opioid misuse and chronic pain in primary care.
Number of Subjects	The target sample size is 260 participants enrolled (200 + oversampling by 30% for attrition) to provide 80% probability that a two-sided 95% confidence interval will have a margin (half-width) less than +/18 standard deviation for the between-groups difference in the study outcomes.
Main Inclusion Criteria	Age ≥18 with a chronic pain-related diagnosis, reporting current pain ≥3 on a 0-10 scale, currently taking prescription opioids for ≥3 months, and surpassed a validated cutpoint for opioid misuse on the Current Opioid Misuse Measure (COMM).
Intervention	Mindfulness-Oriented Recovery Enhancement (MORE) is a group behavioral intervention that unites mindfulness training, cognitive reappraisal, and positive psychological principles into an integrative intervention strategy targeting mechanisms of pain and opioid misuse.
Duration of Intervention	8 weeks.

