## 2. AIMS

AIM 1. To conduct a RCT of the Mindfulness-Oriented Recovery Enhancement (MORE) intervention for co-occurring aberrant drug-related behaviors and chronic pain in primary care.

We will compare the therapeutic impact of MORE and a conventional supportive group (SG) psychotherapy active control condition on clinical outcomes germane to opioid misuse and chronic pain. Hypotheses: Opioid misusing patients assigned to MORE, as compared to SG participants, will evidence decreased opioid misuse and pain (*PRIMARY OUTCOMES*), as well as reduced opioid craving, opioid dosing, and psychological distress (*SECONDARY OUTCOMES*) from pre- to post-treatment through 9-month follow-up.

AIM 2. To test and quantify the degree to which MORE's impact on opioid misuse and pain is mediated by proactive control over emotion-cognition interactions (top-down mechanism).

Hypotheses: The impact of MORE on opioid misuse and pain will be mediated by improvements in: **a)** attentional disengagement from opioid-related cues (reduced attentional bias); **b)** emotion regulation; and **c)** cognitive coping (e.g., reinterpretation of pain as innocuous sensory information).

AIM 3. To test and quantify the degree to which MORE's impact on aberrant drug-related behaviors is mediated by restructuring of reward processing (bottom-up mechanism).

Hypotheses: The impact of MORE on aberrant drug-related behaviors will be mediated by restructured reward processing, as indicated by **a)** decreases in psychophysiological indices of opioid cue-reactivity; **b)** increases in responsiveness to natural reward cues; and **c)** a shift in the relative salience of these cues.

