## 3. STUDY DESIGN

A two-arm parallel RCT design with an active control group will minimize internal threats to validity. Mindfulness-Oriented Recovery Enhancement (MORE; n=130) and the Supportive Group Psychotherapy control (SG; n=130) will be equated for time spent in treatment. Assessors will be blind to treatment condition. Target sample sizes were determined via power and precision analyses. The unit of randomization is the individual patient. The co-primary outcomes are opioid misuse and chronic pain symptoms. Participants will complete a clinical assessment battery at pre- and post-treatment, and at 3-, 6-, and 9-month follow-ups. Participants will complete a psychophysiological assessment protocol at pre- and post-treatment. Participants will complete ecological momentary assessments (EMAs) of symptoms, skill practice, and opioid use during treatment and 1 month afterward up to 3 times/day (morning, noon, and night).

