## 5. RANDOMIZATION

## 5.1 Method of Randomization

An electronic random number generator will randomize participants with simple random assignment in blocks of varying sizes (2 - 4) to preserve unpredictability of allocation, which will be concealed by opaque envelopes.

All participants who met trial eligibility criteria were randomized via simple random assignment.

A computerized random number generator produced the simple random assignment. An investigator uninvolved in recruitment, consenting, assessment, or follow-up generated the assignment. No one else from the trial was involved in the process. To minimize the risk of selection bias, the investigator who generated assignments had no contact with or knowledge of study participants at the time of random assignment.

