## **5.2** Allocation Concealment

Allocation concealment is an important consideration for randomized trials to control for selection bias. To prevent bias and maintain allocation concealment, participants will not be allocated until the day of the first treatment session. Assessments will be conducted by project staff blinded to group assignment (which remained concealed throughout the study). To maintain blinding, the allocation list was inaccessible to project staff involved in assessment or treatment, and before each assessment, participants were reminded to not reveal anything that would disclose their treatment assignment to study staff.

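### Both arms are treated in groups, but the primary BPI and DMI models carry only a patient random intercept, so the .0167 tests are liberal if outcomes correlate within therapy groups

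*SAP*

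**What the plan says.** The synopsis states that "Mindfulness-Oriented Recovery Enhancement (MORE) is a group behavioral intervention that unites mindfulness training". Aim 1 (SAP section 2) names the comparator as a "conventional supportive group (SG) psychotherapy active control condition". Section 3 adds that the "Supportive Group Psychotherapy control (SG; n=130) will be equated for time spent in treatment", and also that "The unit of randomization is the individual patient".

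Section 8.3 describes the primary analyses as "linear and nonlinear mixed models with fixed effects consisting of a time factor and between-subjects treatment factor (MORE vs. SG"), adjusted for baseline.

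- **BPI, model (1):** the indices are individual, outcome, arm and time. The random terms are one patient intercept and a within-patient residual, either diagonal or AR1.
- **DMI:** a logistic mixed model with one patient intercept, independent and identically distributed across patients.

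In both models the index g is the treatment arm. The BPI contrast is the average over four post-randomisation visits, tested at .05/3 = .0167 with Kenward-Roger degrees of freedom. The DMI contrast averages the same four occasions on the logit scale.

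**The concern.** Patients in one therapy group share sessions and peers, so their outcomes may be correlated even though each was randomised individually. A patient random intercept accounts for repeated measures on one person. It does not account for correlation between different people in the same group.

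Nothing else in section 8.3 covers this:

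- Kenward-Roger adjusts for estimating the variance components that are in the model. It cannot restore one that was left out.
- The BIC choice is between within-patient error structures.
- Variations a to f add outcomes, covariates or a different handling of baseline, and the selection model changes the missing-data assumption. All of them keep patients independent, so the three reported p-values could agree and all be too small.

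At stake is the type I error that the plan sets out to control with two-sided tests and a Bonferroni split. The planned models also cannot estimate the within-group correlation, so they cannot show that it is negligible.

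**Working it through.** **1. The plan's own figures.** .05/3 = .0167. For the DMI, a two-sided two-proportion z test of 68% versus 32% with 100 per arm (the N = 200 of section 6.2) has power .9996 at .05 and .998 at .0167. The stated power above .99 reproduces, with patients treated as independent.

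**2. Level of the BPI test when therapy group is ignored.** Assumptions, not in the SAP: m = 6 to 12 analysed patients per group in both arms, and ICC = between-group share of the variance of the baseline-adjusted four-visit average.

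DEFF = 1 + (m - 1) x ICC; level = 2 x [1 - Phi(2.394 / sqrt(DEFF))].

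| ICC | DEFF, m = 6 | level | DEFF, m = 12 | level |
|---|---|---|---|---|
| 0 | 1.00 | .0167 | 1.00 | .0167 |
| .01 | 1.05 | .0195 | 1.11 | .0231 |
| .02 | 1.10 | .0225 | 1.22 | .0302 |
| .05 | 1.25 | .0323 | 1.55 | .0545 |

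A simulation of 20,000 null trials per setting, with about 125 patients per arm, agrees. The patient-level test rejects in .040 of trials at m = 8, ICC .05 (formula .039). A test on therapy-group means stays at .015-.018.

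**3. Fading.** "Participants will complete a clinical assessment battery at pre- and post-treatment, and at 3-, 6-, and 9-month follow-ups", so three of the four averaged visits come after treatment has ended. Take a single-visit ICC of .02 and visit weights w for the group effect. The group variance in the average is b = .02 x (mean w)^2. The baseline-adjusted variance of the average is V = (1 + 3 rho)/4 - rho^2, with rho = .34 to .56 from section 6.2, so V = .389 to .356. Effective ICC = b/(V + b).

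- Undiminished (1, 1, 1, 1): ICC .049-.053, level .032-.057.
- Halving at each visit (1, .5, .25, .125): ICC .011-.012, level .020-.025.
- Post-treatment only (1, 0, 0, 0): ICC .003-.004, level .0175-.019.

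**4. DMI.** Null simulations of the SAP's logistic model move the same way. They assume a patient-intercept SD of 1.0-1.8 and misuse of 34-50%, with ICC as a share of the patient-intercept variance. Levels are .016-.018 at ICC 0, .019-.026 at .02 and .024-.042 at .05. At the pilot effect, dividing 100 per arm by DEFF leaves power at .0167 of .991 (DEFF 1.22) or .965 (DEFF 1.55).

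**5. Precision cost of a group-level reference, BPI, N = 250.** Groups number about 250/6 = 42 or 250/12 = 21. On groups - 2 = 40 or 19 df the critical value is 2.499 or 2.625, against 2.410 on 248 df.

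- ICC 0: 2.499/2.410 = 1.04; 2.625/2.410 = 1.09.
- ICC .02: 1.037 x sqrt(1.10) = 1.09; 1.089 x sqrt(1.22) = 1.20.
- If about 21 or 10 cohorts set the df (20 or 9; critical value 2.613 or 2.933): 8-22% wider at ICC 0 and 14-34% at ICC .02.

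**6. Power at .0167, assumed d = .50 on the averaged BPI outcome** (noncentral t, noncentrality d x sqrt(n / (2 DEFF)), n per arm):

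| N | patient df, ICC 0 | groups - 2 df, ICC 0 | groups - 2 df, ICC .02 | patient df, ICC .02 |
|---|---|---|---|---|
| 250 | .94 | .90-.92 | .82-.89 | .88-.91 |
| 200 | .87 | .79-.84 | .69-.79 | .78-.83 |

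The last column isolates the loss due to clustering itself. The rest of the drop is the price of fewer degrees of freedom.

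**The case against.** **The size is assumed.** Group size, number of groups and ICC are not in the SAP. A reader might infer that the primary tests are in fact inflated two- or threefold. The document does not support that: at ICC 0 there is no inflation, and with fading the level may be only .0175-.025. Levels above .03 need a larger ICC, an undiminished group effect or the largest assumed groups. This objection stands, so the point is conditional.

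**Shared cohorts.** Section 5.1 randomises "in blocks of varying sizes (2 - 4) to preserve unpredictability of allocation", and section 5.2 says "participants will not be allocated until the day of the first treatment session". Each enrolment cohort may therefore have been split into a MORE and an SG group, although the SAP does not say so. Effects that both arms share equally do not inflate the test: with a cohort ICC of .05 and no group effect, the simulated BPI level was .014-.015. This stands, and it affects the remedy.

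**Protocol content.** How groups were formed may be described in the protocol, which is not at hand. Its absence from the SAP is not counted here. The missing model term is a SAP matter, because section 8.3 writes the models out in full.

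**The remedy is not exact.** In simulation the BPI model with a group intercept had level .010-.016 for independent groups. With cohort and group intercepts it was .010-.022 over all cells. For the DMI, t tests on group means or paired cohorts were simulated, but the logistic model with a group intercept was not. No exact degrees-of-freedom rule can be claimed for it.

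**Timing.** Recruitment has ended, and parts of section 8.3 are in the past tense. Whether a change to the primary model would still be pre-specified cannot be judged from the SAP.

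**Conclusion.** The concern holds in conditional form and should be fixed. Both arms are group-delivered, the primary models treat patients as independent, and no planned analysis relaxes this. With positive within-group correlation the .0167 tests exceed their level. On the assumed 6 to 12 patients per group, the excess is small at ICC .01, up to nearly double at .02, and about two- to threefold at .05.

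The two BPI outcomes are the more exposed. A reader might also infer that the DMI result is in doubt. The plan's pilot figures do not support that, because an effect near 68% versus 32% keeps power of .965 or more at the design effects examined. Confidence in the missing term is high. Confidence in its practical size is moderate at best, since it depends on figures the SAP does not give.

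**What to change.** - Add a random intercept for therapy group (patients treated together within one arm) to model (1), keeping Kenward-Roger degrees of freedom.
- Add the same intercept to the DMI model, with a small-sample reference based on the number of therapy groups rather than patients. Check its level by simulation before fixing the rule.
- If each enrolment cohort was split into a MORE and an SG group, add a cohort intercept as well. Without it, the BPI group-intercept model was over-conservative in simulation (.003-.006 at cohort ICC .05 and no group effect).
- Analyse non-attenders in the group to which they were allocated, consistent with intent-to-treat in section 8.1, and report the estimated ICC.
- State beforehand that the specified model is kept if a variance estimate is zero.
- If the primary analysis has already been run, report the clustered model as a sensitivity analysis beside each primary p-value.

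**Cost.** SAP wording and a group identifier (and a cohort identifier, if needed) in the data; no new patients and no change of estimand or alpha. The statistical price is the wider intervals and lower power in steps 5 and 6 of the working. Some of it is paid even at ICC 0, and it is larger if cohorts set the degrees of freedom.

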## 4. ENDPOINTS

The primary, secondary, and tertiary outcome measures are summarized in Table 1.

Event	Screen	Pre -Tx	In	Post-Tx	Follow-Up			
Eveni	Screen	Pie-ix	Tx	POSI-TX	1 Mo	3 Mo	6 Mo	9 Mo
Screening and Stratification Measures								
Informed Consent	X							
Demographics & Medical History	Х							
MINI	Χ							
Primary and Secondary	Outcome N	leasures						
BPI Pain severity and interference		X		×		x	×	X
DMI: ABC, COMM & Urine screen		X		Х		Х	Х	X
Opioid dosing – TLFB and chart review		X		Х		Х	Х	X
DASS Psychological distress		X		Х		х	Х	X
Opioid Craving NRS – EMA (see below)			Х			x		
Mediators								
Self-report mediators: CSQ Reinterpretation FFMQ Mindfulness CERQ Reappraisal WOS Savoring		x		×		X	x	x
Other tertiary measures: PANAS Affect CSQ Pain Catastrophizing MLQ Meaning in Life SHAPS Anhedonia PCL PTSD Self-Transcendence		x		x		х	x	x
Psychophysiological protocol		X		×				

Intervention Process Measures and Ecological Momentary Assessments						
TMS State mindfulness (after			Х			
each session)						
Opioid craving NRS - EMA			X		X	
Opioid dosing – EMA			Χ		Χ	
Affect NRS - EMA			Χ		X	
Pain Intensity & Unpleasantness NRS - EMA			Х		x	
Therapeutic skill practice			Χ		Х	

The primary outcome is opioid misuse measured by the Drug Misuse Index, operationalized as scores on the COMM and triangulated by blinded clinical interview and urine drug screen. The co-primary outcome is chronic pain symptomology, operationalized as pain severity and functional interference scores on the Brief Pain Inventory (BPI). Overall success of the intervention will occur if opioid misuse decreases and pain functioning improves, while pain severity does not worsen. For conservatism, we evaluate all outcomes with two-sided tests, and the Bonferroni correction to control for multiple comparisons.

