Primary outcomes (PRE/POST/FOLLOW-UP). Our pre-specified primary **opioid misuse** outcome in clinicaltrials.gov is a validated composite measure - the Drug Misuse Index (DMI).11 Because there is no single way to identify patients who misuse opioids. 12 the DMI uses 3 levels of data to triangulate opioid misuse: self-reports on a structured questionnaire (i.e., the COMM); clinical assessment of opioid misuse—the Addiction Behaviors Checklist (ABC)—rated by clinical staff (i.e., psychologists, social workers, and nurses) blinded to treatment assignment; and urine toxicology screens. The COMM consists of 17 items rated on a Likert scale (0=never. 4=very often) regarding how often in the past 30 days patients engaged in opioid misuse-related behaviors (e.g., used opioids in ways other than prescribed). COMM scores ≥9 and ABC scores ≥2 are considered positive. A positive rating from the urine screen is given when subjects test positive for illicit drugs or a non-prescribed opioid. Subjects with positive COMM scores will be given a positive DMI and classified as a misuser. If patients deny engaging in opioid misuserelated behavior (COMM scores <9), then positive ratings on both the urine screen and the ABC are needed for a positive DMI, because urine screens can be inaccurate due to variable drug metabolites, and clinician ratings may unreliable. 14,15 Otherwise, subjects will be given a negative DMI. Multiple studies support the validity of this DMI scoring method. 11,16–18 **Chronic** pain symptoms (pain severity and functional interference) will be assessed with the Brief Pain Inventory (BPI).

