## 6.2 Sample Size Determination

The table indicates the smallest detectable effects for a treatment X time interaction term given different sample sizes, assuming a Type I error rate of .05 and varying correlations between repeated measures, which ranged from .34 -.56 per outcome in the R03. Cohen defined f=0.10 and f=0.25 as small and medium effects, respectively. Thus our target N of 260 (N=200 + oversampling by 30% for attrition) will allow us to detect small-to-medium effects on continuous outcomes. Based on dichotomous clinical classification of opioid misuse data from the R03 (68% improvement for MORE versus 32% for SG), the proposed sample size will offer outstanding power (>.99) to detect differences of this magnitude on this outcome. (b) *Precision* of parameter estimation. Our target N will allow model parameters to be estimated with a high degree of precision. A per group sample size of N=130 provides 80% probability that a twosided 95% confidence interval will have a margin (half-width) less than +/- .18 standard deviation. Thus the proposed sample will provide precision more than adequate for estimating small clinical effects with high confidence. (c) *Multivariate models*. Generally, structural equation power calculations for the full information maximum likelihood sensitivity analyses can be based on Root Mean Square Error of Approximation (RMSEA) comparisons of nested models. The proposed sample provides, in a realistic testing scenario, greater than 80% power in a 1 df test (26 versus 25) of close fit comparing two models with RMSEA of .06 and .05 at  $\alpha$ =.05. These calculations are conservative. Maximum likelihood techniques retain all observations at all times, and efficiently incorporate correlated observations to yield an Effective Sample Size that is quantifiably larger than the number of subjects. With fully specified repeated dimensions, the anticipated correlations will yield an effective sample size that is 40% larger, or roughly N=360.

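### Baseline DMI is constant, but pre-treatment COMM severity is not: it is already collected, largely determines the DMI, and enters no DMI analysis

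*SAP*

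**What the plan says.** **DMI model.** Section 8.3 specifies a logistic mixed model "with time t and group g as categorical factors and a random intercept". It has group, time and their interaction, and no baseline term. The reason given is that "it is not necessary to adjust for baseline differences, as all participants exhibited opioid misuse at baseline". The opening sentence of 8.3 promises baseline adjustment for misuse and pain alike, and section 8.2 explains that this adjustment is meant to deal with chance imbalance after randomization.

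**The available score.** Entry requires exceeding the COMM cutpoint (synopsis, main inclusion criteria). Table 1 in section 4 schedules "DMI: ABC, COMM & Urine screen" at pre-treatment. In the DMI scoring rule, "Subjects with positive COMM scores will be given a positive DMI and classified as a misuser"; with a negative COMM, the urine screen and the clinician rating must both be positive.

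**Sensitivity analyses in 8.3.** Variation (a) gives each primary outcome its own baseline value, (b) adds opioid dose and distress, (c) adds gender and age, and (d-f) replace baseline regression with equal baseline means. None names COMM.

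**Missing data.** Section 8.3 says the primary analysis "achieves unbiased estimates of model parameters when missingness arises from processes that depend on observed covariates". It then adds a selection model, reported as p_NMAR.

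**The concern.** A constant binary baseline says only that everyone lies on the same side of a threshold. Two arms that are both wholly DMI-positive can still differ in how far above the threshold their patients started, and that plausibly predicts who falls below it later. The plan adjusts each pain outcome for its own baseline to remove such imbalance, and then exempts the DMI on a ground that does not address severity.

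Three things are at stake, in this order:
- precision of a primary comparison tested at .0167, if the true effect is smaller than in the R03 pilot;
- correction of chance imbalance in severity;
- some protection if severe misusers leave one arm more than the other, because the primary DMI model contains neither a covariate nor a baseline occasion.

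**Working it through.** **1. The plan's own power figure.** Section 6.2 states power above .99 for "68% improvement for MORE versus 32% for SG". With n per arm, difference d = .36, mean proportion .5 and p1q1 + p2q2 = .4352:

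power = Φ[(d√n − z√(2 × .5 × .5)) / √.4352]

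- n = 100, alpha .05: (3.6 − 1.960 × .707)/.660 = 3.36, power .9996.
- n = 100, alpha .0167: (3.6 − 2.394 × .707)/.660 = 2.89, power .998.

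The stated figure reproduces, also at the Bonferroni level.

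**2. Room for variation in COMM.** There are 17 items scored 0 to 4, so the maximum is 17 × 4 = 68. The cutpoint is 9. Enrolled COMM-positive patients can therefore score 9 to 68. The SAP gives no baseline distribution.

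**3. Chance imbalance.** The SE of the arm difference in standardised COMM is √(2/n) = .141 SD at 100 per arm, with a 95% range of ±1.96 × .141 = ±.28 SD. In simulation (person-level logit, 1,500 trials per setting) the unadjusted log odds ratio moved by .55 to .60 per SD of imbalance at an assumed correlation of .34. An imbalance at the edge of that range multiplies the odds ratio by exp(.277 × .55) = 1.16 to exp(.277 × .60) = 1.18. At a correlation of .56 the factor is 1.28 to 1.31.

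**4. Which correlation to assume.** The SAP gives none between baseline COMM and later misuse. Section 6.2 cites only "varying correlations between repeated measures, which ranged from .34 -.56 per outcome in the R03". If those come from patients not selected on COMM, selection above the cutpoint shrinks them. With COMM taken as half-normal above the cutpoint (SD .603, variance .363):

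r′ = .603r / √(.363r² + 1 − r²)

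so .34, .45 and .56 become .21, .29 and .38.

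**5. Power without and with COMM.** The setting is a random-intercept logistic model with the main effect averaged over four visits, 100 per arm, alpha .0167, SG 32% improved, latent follow-up correlation .45 (assumed), and both models fitted to the same simulated data.

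| MORE vs SG improved | r | Without COMM | With COMM |
|---|---|---|---|
| 47% vs 32% | 0 | .785 | .784 |
| 47% vs 32% | .21 | .788 | .810 |
| 47% vs 32% | .29 | .794 | .840 |
| 47% vs 32% | .34 | .797 | .859 |
| 47% vs 32% | .38 | .795 | .874 |
| 55% vs 32% | .34 | .989 | .995 |
| 68% vs 32% | .34 | 1.00 | 1.00 |

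Over r = .21 to .38 the gain at 47% versus 32% is 2 to 8 points (paired Monte Carlo SE at most .006). At r = .45, above that range, it is 11 points. A repeat simulation gave .783/.810 at r = .21 and .781/.852 at r = .34.

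**6. Type I error under dropout.** The planned loss comes from "oversampling by 30% for attrition": 60 of 260, or 23%. The simulation uses 250 enrolled, 125 per arm, with no treatment effect. Dropout odds are assumed to double per SD of COMM. Nominal level .0167, simulation SE about .0025.

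| Dropout pattern | Without COMM | With COMM |
|---|---|---|
| Unrelated to COMM (r = .34) | .020 | .022 |
| Related equally in both arms | .018 | .021 |
| MORE only, all lost before post-treatment, r = .21 | .022 | .017 |
| same, r = .34 | .025 | .020 |
| same, r = .45 | .032 | .018 |

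With the same 23% spread over the four visits (MORE only), the unadjusted error was .018 at r = .21 and .022 at r = .34; a repeat run gave .01 to .02. This is expected: a patient who leaves later has already contributed DMI observations, which the mixed model uses.

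**7. Wording of the sensitivity variations.** Two arms by four visits need 8 design columns. A constant baseline DMI makes 9 columns with rank still 8, so in a-c it adds nothing. In d-f a baseline proportion of 1 has no finite logit. Dropping the term leaves the treatment contrast and the 3 df test unchanged.

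**The case against.** The strongest reply is that 8.3 keeps to its own rule. The rule is to covary the baseline level of the outcome; the outcome is the binary DMI, and that is constant. COMM is a component, not the outcome. The unadjusted randomised comparison is valid, so adding a prognostic covariate looks like preference. This stands as far as validity goes. It does not meet the purpose stated in section 8.2, which is to correct chance imbalance, and which a constant score cannot serve.

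Second, the power gain needs an effect below those reported from the pilot. Section 6.1 cites d = .50 to .84. Starting from 32%, d = .50 corresponds to about 51% (probit scale) to 54% (logit scale), close to the 55% case where COMM adds less than 1 point. This stands: the gain of 2 to 8 points is insurance against a smaller effect.

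Third, the dropout figures put all loss before post-treatment, which the SAP does not say, and nothing in the SAP suggests that dropout depends on COMM differently by arm. Section 8.3 also has the selection model and the correlated dose and distress variables. This largely stands: those analyses give partial protection, and the dropout argument is secondary.

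A reader might go further and infer that the primary DMI test is biased or its error rate seriously inflated. The document does not support that. Simulated error reaches .033, .048 and .076 (r = .21, .34, .45) only if severe misusers leave one arm while mild ones leave the other, all before post-treatment, which is an extreme assumption.

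**Conclusion.** The point holds as a matter of precision and chance imbalance. The reason given in 8.3 justifies leaving out baseline DMI; it does not justify leaving out baseline severity, for which a score is in hand.

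The size is moderate and conditional. There is no gain at 68% versus 32%, under 1 point at 55%, and about 2 to 8 points at an assumed 47% with r between .21 and .38. A chance imbalance at the edge of its 95% range would move the odds ratio by a factor of about 1.16 to 1.18 at r = .34. Under MORE-only dropout the unadjusted type I error is about .02 to .03 (r = .21 to .45) if everyone leaves before post-treatment, and close to nominal if loss is spread over the visits.

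The smaller effect, the correlations, the half-normal COMM distribution and the dropout patterns are all assumptions. It should not be inferred that the trial is underpowered for its planned effect or that the unadjusted test is invalid. Nor does the missing DMI exemption in variations a-f alter any result.

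**What to change.** - Add the continuous pre-treatment COMM score as a prespecified covariate in the DMI logistic mixed model, and for the DMI in variations a-c.
- Date the change against data access. Recruitment has closed and parts of 8.3 are in the past tense, so if outcome data have been seen, run it as a labelled supplementary analysis and leave the primary model as it is.
- Reword 8.3, including its opening sentence, to say that baseline DMI is constant and that pre-treatment COMM is used in its place.
- State that the DMI odds ratio is then conditional on COMM as well as on the random intercept. It will generally lie further from 1 than the unadjusted one: in the person-level simulation at 68% versus 32% and r = .34, the log odds ratio went from −1.52 to −1.65.
- As a wording edit with no effect on results, say that the DMI has no baseline DMI term in a-c and no baseline constraint in d-f.

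The cost is SAP text and one covariate already collected. No new data are needed, and neither the sample size nor alpha changes.
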